### Subgroup analyses

The following prespecified subgroups will be analysed to evaluate the heterogeneity of any treatment effect.

- Age above/below median age
- Sex (male vs. female)
- Anticoagulation therapy (yes/no)
- Albumin level (over and under mean level)
- LVEF (over and under mean level)
- Severe chronic kidney disease (eGFR < 30) (yes/no)

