### Statistical principles

All outcomes are tested for superiority. A two-sided p-value  $<0.05$  is considered statistically significant, and a 95% confidence interval (CI) is reported for all effect estimates. No multiplicity adjustment will be applied.

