### Baseline characteristics

Baseline patient characteristics and demographics will be reported for each group (Table 1 in the final publication).

Table 1: Baseline characteristics

Variable	Data type
Demographics	
Age (years)	Continuous
Sex (female) %(n)	Categorical
Race (white)	Categorical
Included at specialised referral centre %(n)	Categorical
Symptoms and physical examination	
Height (cm)	Continuous
Weight (kg)	Continuous
BMI (kg/m  )	Continuous
Rales %(n)	Categorical
Peripheral oedema %(n)	Categorical
Orthopnoea %(n)	Categorical
Ascites %(n)	Categorical

NYHA class %(n)	Categorical, ordinal
II	
III	
IV	
Fatigue %(n)	Categorical
The CSHA clinical frailty scale score [9,10]	Categorical, ordinal
Score<4 = frail %(n)	
Score>4 = not frail %(n)	
Heart failure characteristics	
LVEF (%)	Continuous
Time since HF diagnosis (months)	Continuous
New-onset HF %(n)	Categorical
Ischemic aetiology %(n)	Categorical
Medical history	
Cardiovascular comorbidities %(n)	Categorical
Atrial fibrillation	
Hypertension	
Comorbidities %(n)	Categorical
COPD	
Diabetes	
CKD	
Liver disease	
Smoking (former or active) %(n)	Categorical
Alcohol over 7 /14 units pr. week (woman/men) %(n)	Categorical
Laboratory values	
Haemoglobin mmol/L	Continuous
Sodium mmol/L	Continuous
Potassium mmol/L	Continuous
Creatinine micromole/L	Continuous
eGFR (mL/min/1.73m  )	Continuous
NT-proBNP (pmol/L)	Continuous
Albumin g/L	Continuous

Troponin T/I above the upper reference limit %(n)	Categorical
C reactive protein mg/L	Continuous
Treatment	
ACEi/ARB/ARNI %(n)	Categorical
Beta-blockers %(n)	Categorical
MRA %(n)	Categorical
SGLT2i %(n)	Categorical
Home loop diuretics %(n)	Categorical
Home loop diuretics dose (furosemide-equivalent dose, mg daily)	Continuous
Anticoagulant therapy %(n)	Categorical
VKA	
DOAC	
LMWH	
ICD %(n)	Categorical
CRT %(n)	Categorical

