### Statistical methods to compare primary and secondary outcomes between groups

#### Main analysis of primary outcome

The primary outcome of the trial, “days alive without hospitalisation during the 90 days following randomisation”, is a countable outcome with an anticipated non-normal distribution.

Accordingly, we plan a non-parametric analysis of the primary outcome [16]. We will assess the Mann-Whitney parameter using the Wilcoxon-Mann-Whitney-test on the full analysis dataset according to the intention-to-treat principle [17].

For explorative purposes, the analysis will also be performed on the per-protocol dataset and as-treated dataset.

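### Heterogeneity is to be evaluated by cutting age, albumin and LVEF at the sample median or mean, and no interaction estimate is specified for any of the six subgroups

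*SAP*

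**What the plan says.** The SAP section Subgroup analyses opens with its aim: "The following prespecified subgroups will be analysed to evaluate the heterogeneity of any treatment effect". Six factors follow. Three are cut from continuous measurements at a value taken from the trial's own data: "Age above/below median age", "Albumin level (over and under mean level" and "LVEF (over and under mean level". The others are sex, anticoagulation (yes/no) and eGFR below 30. The section names no outcome, test, estimate or model.

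The Baseline characteristics table lists all three split variables as continuous, for example "Albumin g/L Continuous". For the primary outcome the SAP states: "We will assess the Mann-Whitney parameter using the Wilcoxon-Mann-Whitney-test on the full analysis dataset according to the intention-to-treat principle". The van Elteren tests under Sensitivity analyses are the only other named tests for that outcome. Statistical principles adds "A two-sided p-value $<0.05$ is considered statistically significant", requires a 95% CI for every effect estimate, and closes with "No multiplicity adjustment will be applied". No interaction test or interaction estimate appears anywhere in the SAP.

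**The concern.** The question asked is whether the treatment effect varies with a patient characteristic. Two features of the plan weaken the answer.

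First, replacing a measured age, albumin or LVEF by high versus low discards how the effect changes along the scale. It treats patients just above and just below the cut as different, and patients at the extremes as the same as those near the cut. The cut values are known only after enrolment, and no reason is given for using the median for one variable and the mean for two.

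Second, neither the Wilcoxon-Mann-Whitney test nor the van Elteren test yields a treatment-by-modifier estimate, and nothing else is specified to supply one. An analyst who simply applied the named test within each part would obtain two p-values per factor. A difference between two p-values is not evidence that two effects differ. At stake is a secondary claim of benefit confined to, say, older patients or those with low albumin. The primary result is not touched.

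**Working it through.** **Inputs.** From Sample Size: 126 participants, 3-day difference, SD 5 days, two-sided α 0.05, power 90%, in-hospital mortality 5%. From Study design: 1:1 allocation, hence 63 per arm. The subgroup section gives no figures. Equal halves (about 31.5 per arm), a normally distributed modifier and a linear interaction are assumptions made here.

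**Reproducing the plan's figure.** The standardised difference is 3/5 = 0.6. A two-sided t-test at 0.05 with 90% power needs 59.35, rounded up to 60 per arm, or 120 in total. A 5% allowance gives 120 × 1.05 = 126, or 120/0.95 ≈ 127. The stated 126 is therefore reproduced with the 5% allowance, although the SAP does not show that step. The inputs can be carried forward.

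**Information kept after a split.** For a normal modifier cut at its median and an interaction linear in it, the relative efficiency is 2/π = 0.64, a loss of 36%. An interaction test with 80% power on the continuous scale has a standardised signal of 1.96 + 0.84 = 2.80. After the split:

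Φ(2.80 × √(2/π) − 1.96) = Φ(2.80 × 0.798 − 1.96) = Φ(0.27) = 0.61.

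The 80% is a hypothetical starting point. A simulation at the trial's size (63 per arm, SD 5, mean effect 3 days, 4,000 runs, linear model) gave:

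| Assumed slope of the effect | Continuous term | Median split |
|---|---|---|
| none (false-positive rate) | 5.3% | 5.5% |
| 1.5 days per SD of modifier | 39% | 27% |
| 2.5 days per SD of modifier | 77% | 57% |

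**If the halves were compared by significance.** With 90% power overall the standardised signal is 1.96 + 1.28 = 3.24. In a half-sample with the same true effect:

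Φ(3.24 × √0.5 − 1.96) = Φ(0.33) = 0.63.

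The chance that exactly one half is significant is 2 × 0.63 × 0.37 = 0.47. The t-test calculation at 31.5 per arm gives power 0.65 and 2 × 0.65 × 0.35 = 0.46. Simulated Wilcoxon tests also gave 46%. With no effect in anyone the same chance is 2 × 0.05 × 0.95 = 9.5%, against 5% for one interaction test.

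**What an interaction test can do here.** For the difference in effect between two halves, the standard error is 5 × √(4/31.5) = 1.78 days. Power for a 3-day interaction is Φ(3/1.78 − 1.96) = 39%. The interaction detectable with 80% power is 2.80 × 1.78 ≈ 5.0 days. Over six factors at an unadjusted 0.05, the chance of at least one false positive is 1 − 0.95⁶ = 26% if they were independent, which they probably are not.

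**The case against.** A reader might infer that the SAP has chosen to judge heterogeneity by comparing p-values within subgroups. The document does not support that. It is silent on method, so the 46–47% is conditional on a practice it never proposes. Nor does the choice of a rank test force separate tests. The Mann-Whitney parameter is an estimate with a 95% CI, and two independent subgroup estimates can be contrasted directly. The section also names no outcome, and for time-to-event outcomes the SAP already provides proportional hazards regression, which can carry an interaction term. This part of the objection stands. On its own, the absent interaction test would be missing detail rather than an error.

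A reader might also infer that data-derived cuts can be picked to suit the result. They cannot: the rule is fixed in advance, and the realised cut can be reported and reused elsewhere. Values equal to the cut have no stated group, but this matters mainly for age in years at its median, because a mean will seldom coincide with a recorded value.

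The quantities rest on assumptions that the SAP does not supply. Mean splits need not give equal halves. Eligibility caps LVEF at 45%, so normality is doubtful there. The outcome is bounded at 0 and 90, with in-hospital deaths during the index admission set to 0. Median and mean splits are also common for display.

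What the objection does not answer is that dichotomisation is stated, not inferred, for three variables recorded as continuous, under an explicit aim of evaluating heterogeneity. That choice loses information whichever method is then applied to the two parts.

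**Conclusion.** The point holds as a worthwhile, inexpensive improvement to a secondary analysis. The stated splitting of age, albumin and LVEF costs roughly 36% of the information on a linear interaction (80% power falling to about 61%), given a normal modifier cut at its median. For the mean splits, and for LVEF in particular, that figure is approximate. The splitting criticism does not extend to sex, anticoagulation or eGFR below 30, but the lack of a specified interaction estimate affects all six factors.

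The risk of a spurious contrast, about 46–47% per evenly split factor under a uniform effect, is illustrative. It arises only if significance is compared between the parts, which the SAP neither states nor excludes. Even a well-specified interaction analysis will be imprecise at 126 participants, which argues for reporting estimates with intervals.

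**What to change.** Amend the subgroup section as follows:

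- Name days alive outside hospital as the outcome for the heterogeneity analysis.
- For each of the six factors, prespecify a treatment-by-modifier interaction estimate with 95% CI and p-value, for example from a probabilistic-index or proportional-odds model.
- Enter age, albumin and LVEF as continuous terms.
- Keep the median and mean cuts for tables or a forest plot only, report the realised values, and assign values equal to the cut to one named group.
- Base any statement about heterogeneity on the interaction and not on significance within a subgroup.
- Label the results exploratory, given six factors and no multiplicity adjustment.

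The cost is a paragraph of SAP text and one model per factor, on baseline data already listed for collection. The downside is a linear-trend assumption for the continuous terms and, if that model is used, a proportional-odds assumption for a bounded outcome with deaths at zero; both can be examined. The primary analysis does not change, and low interaction power is not cured.

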### Harms

Both treatment strategies are established practices with known side effects and complications. The study is not powered to investigate the comparative effectiveness of the intervention and comparator regarding safety and harm. The number of complications to interventional thoracentesis in the intervention group and complications during the index admission in both groups will be assessed as secondary outcomes, as specified in Table 2.

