## Trial population

Eligibility criteria are stated in the study protocol version 2.0 (January 7th 2022). The criteria have been updated with minor changes from version 1.0 (December 21st 2021). Primarily one additional exclusion criterion was added “planned or expected admission >10 days for other condition than heart failure”, and two exclusion criteria were clarified: “Known or suspected malignant disease” was changed to “clinically indicated diagnostic thoracentesis (e.g. suspected malignant aetiology)” and “eGFR<15ml/min/1.73m^2 or acute renal failure” was changed to “eGFR<15ml/min/1.73m^2 or dialysis treatment”. Eleven participants were included under the criteria in protocol version 1.0. The impact of the changes in eligibility criteria is

believed to be minor, and we do not see the need for stratification of the population based on whether they were included before or after the implementation of protocol version 2.0.

The following will be reported.

- The number of patients screened for eligibility with an explanation for the exclusion
- The number of patients randomised
- The number of participants allocated to each group.
- The number of participants that followed the treatment strategy according to the protocol (patients in the intervention arm being referred to upfront thoracentesis by the treating physician (scheduling when the thoracentesis will be performed) and patients in the control arm who are not referred to thoracentesis within five days after randomisation)
- The number of participants that received the planned treatment according to the allocated treatment strategy (thoracentesis performed on participants in the interventional group and thoracentesis not performed on participants in the control group).
- The number of participants in the intervention group that did not have thoracentesis performed and the number of participants in the control group that had thoracentesis.
- The number of participants that withdrew from the trial or were lost to follow-up with an explanation. The level of consent withdrawal will be reported (“consent to continued data collection and questionnaire follow-up”, “consent to continued data collection but no questionnaire follow-up”, “complete – no questionnaire follow-up or data collection”)
- The number of participants analysed for the primary outcome according to the intention-to-treat principle.

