Number of complications to interventional thoracentesis:  - Pneumothorax. - Intrapleural bleeding (haemothorax) - Infection requiring antibiotics (empyema) - Pain/discomfort with the need for analgesics - Organ laceration - Re-expansion pulmonary oedema. - Thromboembolic events within 30 days from discontinued anticoagulation therapy (deep vein thrombosis, pulmonary embolism, ischemic stroke, transient ischemic attack, systemic embolism, myocardial infarction)	Count	From randomisation until the date of discharge from the hospital.
Number of complications during the index admission  - Delirium requiring pharmacological therapy - Fall - Nosocomial infections like pneumonia, urine catheter-related infection, and central venous catheter-related infections requiring a change of the catheter and antibiotic treatment.	Count	From randomisation until the date of discharge from the hospital.
Kansas City Cardiomyopathy Questionnaire score (KCCQ-23)	Scores from 0-100.  100 representing the best outcome.	14 days after discharge from index admission and 90 days after randomisation
Satisfaction with hospital stay - Selected questions from the questionnaire "Questions about your admission" from the annual Danish National Survey of Patient Experiences"	Likert scale from 1-5. 5 represents the best outcome.	14 days after discharge from index admission

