#### Analyses of Secondary Outcomes

The number of days alive and not hospitalised due to heart failure has the same assumptions as the primary endpoint and will be analysed as such. Distribution of the secondary outcome continues variables will be determined by visual inspection of the histogram and by QQ plots. Normally distributed continuous variables will be compared by students' t-test and non-normal distributed continuous variables by the non-parametric Wilcoxon-Mann-Whitney-test. Categorical data will be compared using Chi-squared or exact Fisher test if  $n < 5$  in a group. Time-to-event data will be compared by the log-rank method, and adjusted analyses will be performed by proportional hazards regression. The main analysis of KCCQ scores will be a comparison of the mean score at each time point. For further exploratory analyses, the total KCCQ-score at each time point will be summarized in 25-point ranges, where scores represent health status as follows: 0 to 24: very poor to poor; 25 to 49: poor to fair; 50 to 74: fair to good; and 75 to 100: good to excellent [19].

The number and percentage of complications to thoracentesis will be reported. The number and percentage of thromboembolic events within 30 days and complications during the index admission will be compared between the groups. Results will be presented in tables, and time-to-event outcomes will be illustrated by Kaplan-Meier curves.

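### The SAP is inconsistent on whose thoracentesis complications are counted, and its discharge window omits late procedural events and conflicts with the 30-day thromboembolic component

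*SAP*

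**What the plan says.** **Which arm.** The Harms section sets two counts against each other: "The number of complications to interventional thoracentesis in the intervention group and complications during the index admission in both groups". The table under Outcome definitions and timing of outcome assessment labels the row "Number of complications to interventional thoracentesis" and names no arm. Analyses of Secondary Outcomes is equally open: "The number and percentage of complications to thoracentesis will be reported".

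**Who has the procedure.** Trial population commits to reporting "the number of participants in the control group that had thoracentesis". Under Adherence and protocol deviations and Randomization errors, a control participant is compliant after five days of drug treatment alone, so a thoracentesis after that point is within protocol.

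**Until when.** The assessment time for the thoracentesis-complication row is "From randomisation until the date of discharge from the hospital". The row covers pneumothorax, haemothorax, infection (empyema is named), pain, organ laceration and re-expansion oedema. It also covers "Thromboembolic events within 30 days from discontinued anticoagulation therapy". For that last component and for the separate index-admission complications, the analysis section plans a comparison: "The number and percentage of thromboembolic events within 30 days and complications during the index admission will be compared between the groups".

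**The concern.** The trial compares two strategies, and thoracentesis after an initial period of drug treatment is something that can happen under the control strategy. Secondary objectives lists complications among the outcomes on which the strategies are to be contrasted. If the Harms wording is followed, procedural harm is collected in one arm only. The report could then state how many controls had the procedure but not what happened to them.

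The window raises a separate problem. Discharge falls at a different time for each participant, and some listed events can be recognised after it. Under the row as written, an empyema found after discharge is not a complication of thoracentesis. It could enter the results only as an unlabelled readmission or death.

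What is at stake is the completeness of the safety description. No efficacy result depends on it.

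**Working it through.** **1. The plan's own figure.** The only computed figure is the total of 126 in Sample Size. Inputs: difference 3 days, SD 5 days, two-sided α 0.05, power 90%. The standardised difference is 3/5 = 0.6, and a two-sample t-test then needs 59.35 per arm. Reading the 5% in-hospital mortality as an allowance (my inference), 59.35/0.95 = 62.48, rounded up to 63 per arm, or 126 in total. The figure reproduces. This point uses only the arm size: 126/2 = 63 at 1:1 allocation.

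**2. The sections side by side.**

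| Question | Harms | Outcome table | Analyses of Secondary Outcomes |
|---|---|---|---|
| Arm for procedural complications | Intervention only | Not restricted | Not restricted |
| Window, non-thromboembolic components | Refers to the table | Ends at discharge | Not stated |
| Window, thromboembolic events | Refers to the table | 30 days from stopping anticoagulation, in a row that ends at discharge | 30 days, start not stated |
| Compared between arms? | Not stated | Not stated | Thromboembolic and index-admission events only; the rest are reported |

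Two conflicts follow. Harms is narrower on arm than the other two sections. The row's assessment time disagrees with one of its own components whenever discharge comes before the 30 days are up.

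**3. Scale, on assumed values.** The SAP gives neither a crossover rate nor a complication risk. Let c be the share of controls who have thoracentesis and u the share of the intervention arm who do, with one procedure per treated participant.

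Share of treated participants outside an intervention-only count = 63c / (63c + 63u). With u = 0.90, 63u = 56.7.

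Chance of at least one uncounted control complication = 1 − (1 − p)^m, with m = 63c rounded and p = 5% per treated participant.

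| c | 63c (m) | Share outside the count | Chance of ≥1 uncounted, p = 5% |
|---|---|---|---|
| 5% | 3.15 (3) | 3.15/59.85 = 5% | 14.3% |
| 10% | 6.3 (6) | 6.3/63.0 = 10% | 26.5% |
| 20% | 12.6 (13) | 12.6/69.3 = 18% | 48.7% |
| 30% | 18.9 (19) | 18.9/75.6 = 25% | 62.3% |

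At c = 10–20%, the share outside the count is 11.1–20.0% if u = 0.80 and 9.1–16.7% if u = 1.00. At the same c, the chance of at least one uncounted event is 11.4–23.1% if p = 2% and 46.9–74.6% if p = 10%.

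**4. Effect on the complication rate.** With no events in n procedures, the one-sided 95% upper limit is 1 − 0.05^(1/n). For n = 57 (intervention only) it is 5.1%. For n = 57 + 13 = 70 it is 4.2%. The gain in precision is small; the main gain is completeness.

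**The case against.** The other side has several fair points.

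- **Arm.** The restriction stands in one section only, and that section refers back to a table that carries no restriction. It is therefore not established that control procedures would be missed. Nor does the SAP set control-arm procedural harm to zero: events that are not assessed are not the same as no events. This limits how strongly the point can be put. But the open wording elsewhere does not say that controls are included, and the contrast with both groups in Harms looks deliberate.
- **Window.** A reader might infer that every complication is counted only to discharge. That is wrong: thromboembolic events have a 30-day period and are compared between arms. The omission concerns the other components.
- **Bias.** A reader might infer that the intervention arm is observed for less time and that a between-arm comparison is therefore biased. The SAP does not support this. Length of stay is an outcome under test, not a known effect. Up-front procedures come early in the stay, while compliant controls have none for five days, so time from procedure to discharge need not be shorter in the intervention arm. The non-thromboembolic procedural complications are also only reported, not tested between arms.
- **Late events.** They are not wholly lost. Readmission, death and days alive outside hospital run to day 90 in both arms, though without a procedural label.
- **Importance.** The SAP says that the trial is not powered for harms. This limits inference but does not justify incomplete counting.
- **Other documents.** The table summarises a data-collection procedure that is not at hand and may settle arm and window. The SAP's own sections would still disagree.

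**Conclusion.** The point holds in a limited form. The SAP contradicts itself on which arm's thoracentesis complications are counted. Followed as Harms is written, it leaves out procedures that the SAP itself anticipates in controls. Separately, the discharge window omits late non-thromboembolic procedural events and does not fit the 30-day component in the same row.

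The size of about 10–18% of treated participants outside an intervention-only count rests wholly on assumed control crossover of 10–20% and 90% uptake in the intervention arm. Crossover of 5–30% widens it to about 5–25%. The number of post-discharge events cannot be estimated from the document.

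The consequence is an incomplete description of safety. The primary analysis is untouched, and nothing here shows a biased test. It is worth correcting because the correction is cheap.

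**What to change.** Amend the outcome table, Analyses of Secondary Outcomes and Harms so that all three say the same:

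1. Complications are counted for every thoracentesis in either arm. State until when a procedure qualifies (index admission only, or any time to day 90).
2. Results are given by allocated arm, which describes the strategies, and per procedure performed, which gives the complication rate.
3. Each component has a fixed window that does not depend on discharge. Thirty days from the procedure and day 90 from randomisation are both workable. The shorter one makes attribution to the procedure easier, and the longer one matches the existing follow-up.
4. The discharge and 30-day windows in the thoracentesis row are reconciled, for example by giving thromboembolic events their own row, with the start of the 30 days stated for participants in both arms.

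The cost is SAP wording and some extra data extraction. Records are already searched to day 90 for death and admission days, but the SAP does not say that procedural complications are collected in that search, so the added work is modest and not nil. No new visits or procedures are needed.
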